2.4 Existing Knowledge

An updated Cochrane systematic review of interventions for 1st MTPJ OA is pending.[15] Only one observational study and four clinical trials (n=304) have tested contoured orthoses or shoe-stiffening inserts for 1st MTPJ OA. One trial has measured patient-reported outcomes beyond three months.[6-9]

In 2016, Menz et al [6] compared prefabricated contoured orthoses to rocker-sole shoes (n=104, single-blind, single centre, Australia). There were no differences in foot pain intensity or function at three months. In an Australian private practice randomised trial, Paterson et al [7] compared prefabricated contoured orthoses to sham insoles (n=88), on a primary outcome of 1st MTPJ pain on walking over three months. Prefabricated contoured insoles offered no benefit over sham.[7, 16]

BigTOE Trial Protocol

A small trial from the US (n=13)[8] compared carbon fibre shoe-stiffening inserts against a contoured orthoses with a rigid extension in people with 1st MTPJ OA. Those wearing carbon fibre shoe inserts had lower pain intensity and pain interference scores at six and 12 weeks. Adherence and comfort levels were higher in those wearing carbon fibre shoe-stiffening inserts.

An Australian observational case series (n=31)[17] found improvements in foot pain and disability at one and three months after wearing semi-rigid carbon fibre inserts. These shoe stiffening inserts were then compared to sham inserts in the Australian SIMPLE randomised trial (n=100).[9] The primary outcome, foot pain at three months, was measured using the Foot Health Status Questionnaire pain subscale (FHSQ; 0-100).[9] Shoe-stiffening inserts, compared to sham inserts, reduced joint pain at three months (FHSQ mean difference (MD) 6.66; 95% confidence interval (CI) 0.65 to 12.67; p<0.03) and six months (MD 9.59; 95% CI 2.00, 17.18). At one year, a clinically relevant difference in pain and function was found, favouring shoe stiffening inserts. Participant perception of global improvement was higher in those wearing shoe-stiffening inserts (61% vs 34%, Risk Ratio (RR) 1.73, 95% CI 1.05 to 2.88, number needed to treat (NNT) 4).

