2.7.2 Objectives

- i) To undertake an internal pilot to test and refine trial procedures, and establish screening recruitment processes in secondary and community care;
- ii) Review internal pilot data and recruitment optimisation findings, adapt procedures accordingly prior to rollout to main trial;
- iii) Run a definitive multicentre parallel group, blinded RCT recruiting 438 participants from up to 25 UK centres;
- iv) To conduct a mixed-methods, embedded process evaluation to inform trial recruitment and insole device adherence, reasons for non-adherence;

v) To evaluate the cost-effectiveness of shoe stiffening inserts compared to sham inserts over 12 months follow-up.

3. Trial Design

A multicentre, parallel group, participant-blinded, sham-controlled RCT with internal pilot and embedded process evaluation and economic evaluation.

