3.5.3 Secondary outcomes

People with foot OA report varying levels of painful symptoms and disability and it is important to capture how these impact on HRQoL and daily activities. Health and social care resource use data will be collected for health economic analyses.

Secondary outcomes will be measured at baseline, one, three, six and 12 months after randomisation.

- Foot related QoL: MOxFQ: all subdomains and summary score
- 1st MTPJ pain: average pain intensity (NRS) in the index 1st MTPJ recalled over the last week whilst at rest /walking
- Foot pain: average pain intensity (NRS) in index foot, recalled over the last week whilst at rest/walking
- HRQoL: EQ-5D-5L (VAS & Index)
- Participant reported Global Rating of change (GROC)
- Participant reported insole adherence/ reasons for non-adherence
- Analgesic medication
- Health care resource use
- AEs and SAEs
- Participant reported problems with shoe inserts

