3.5.4 Timing and format of outcome assessments

All measures will be collected at baseline (pre-randomisation), one, **three**, six- and 12-months postrandomisation. Baseline questionnaires can be completed electronically, or on paper in clinic, with help from clinic staff if required, and returned to WCTU. Follow-up questionnaires will be completed remotely online, by telephone, or by post at each time point, and coordinated by WCTU. An email and/or text message will be sent to participants with an electronic link that will take them to the online questionnaire portal. Where participants need support, questionnaires can be completed via the telephone with a member of the WCTU study team for whom treatment allocation is concealed. Reminders will be sent to non-responders after two weeks following WCTU processes. The minimum core data set will include the MOxFQ and EQ-5D-5L at baseline and three months.

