Healthcare resource utilisation data will be collected from baseline to the 12-month follow-up for both groups using CRFs by site staff and by participants using self-report questionnaires during each follow-up assessment. The resource utilisation will aim to capture the key cost drivers associated with 1st MTPJ OA management including the costs of carbon fibre shoe-stiffening inserts, sham inserts, any healthcare visits, hospital admissions and medications. Healthcare resource use will be costed using appropriate cost data from local and national databases in £ sterling to the most relevant price year available at the time of the analysis. Any prices not in that financial year will be reflated to current prices.

To estimate quality-adjusted life years (QALYs), health-related quality of life (HRQoL) will be assessed at baseline, three, six, and 12 months using the EQ-5D-5L instrument. Using the trapezoidal rule, responses will be used to generate QALYs based on the UK value set (scoring algorithm) recommended by NICE at the time of analysis[45].

Descriptive statistics will summarise costs and QALYs by the intervention and comparator groups. The pattern of missing data will be examined and accounted for using suitable methods for multiple imputation. Using a bivariate regression for costs and QALYs, the base-case analysis will be conducted under an intention-to-treat (ITT) approach to calculate the incremental cost-effectiveness ratio (ICER), as the additional cost per QALY gained with carbon fibre shoe-stiffening inserts compared to sham inserts. Non-parametric bootstrapping will generate mean values and 95% confidence intervals (CIs) for costs, QALYs, and the ICER. The results will be presented using the cost-effectiveness planes and cost-effectiveness acceptability curves (CEACs) will be plotted to illustrate the likelihood of carbon fibre shoe-stiffening inserts being cost-effective compared to sham inserts at the typical willingness-to-pay thresholds. Net monetary benefit (NMB) analysis will also be generated, where a positive NMB indicates that the QALYs outweigh the costs. Secondary analyses will include a societal perspective to look at the wider impact on patients and their families. Deterministic and probabilistic sensitivity analyses will be conducted to explore uncertainties surrounding key parameters and

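### Protocol section 9 builds QALYs from EQ-5D-5L at four time points although five are collected; leaving out month 1 without a reason can bias the incremental QALY, modestly and in an unknown direction

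*Protocol*

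**What the plan says.** Section 9 (health economic evaluation) says that, for the QALY, "health-related quality of life (HRQoL) will be assessed at baseline, three, six, and 12 months using the EQ-5D-5L instrument". It continues: "Using the trapezoidal rule, responses will be used to generate QALYs based on the UK value set (scoring algorithm) recommended by NICE". Month 1 is not among the named time points.

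Three other places include month 1:

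- Section 3.5.3 lists EQ-5D-5L (VAS and index) among the secondary outcomes and says: "Secondary outcomes will be measured at baseline, one, three, six and 12 months after randomisation".
- Section 3.5.4 says: "All measures will be collected at baseline (pre-randomisation), one", and goes on to three, six and 12 months.
- Table 2 ticks the EQ-5D-5L row at baseline and at months 1, 3, 6 and 12.

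Section 9 also collects resource use at each follow-up, and Table 2 ticks health and social care resource use at month 1. The cost side of the ratio therefore draws on a visit that the QALY side does not use. The economic objective in section 2.7.2 is "To evaluate the cost-effectiveness of shoe stiffening inserts compared to sham inserts over 12 months follow-up", so the first three months are a quarter of the horizon. A separate health economic analysis plan is still to be written.

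**The concern.** The protocol names a specific set of time points for the QALY, and that set disagrees with its own collection schedule. This is more than detail deferred to a later plan, because the later plan would inherit the four-point rule.

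The trapezoidal rule assumes a straight line between the points it is given. Without month 1, it assumes that utility in each arm moves linearly from baseline to month 3. If the between-group difference appears early, part of the gain is missed. If it appears late, or starts with a loss, the gain is overstated. The incremental QALY is the denominator of the cost-effectiveness ratio and enters net monetary benefit, so any error passes straight into the main economic result. It would arise even though the trial holds data that could reduce it. Leaving the two schedules unreconciled also leaves room to choose between two QALY definitions once results are known.

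**Working it through.** The protocol gives no utility, QALY or area-under-curve figure, so there is no stated result to reproduce. The check is the algebra of the rule itself.

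**Inputs.** The QALY time points are 0, 3, 6 and 12 months (section 9). The collection times are 0, 1, 3, 6 and 12 months (sections 3.5.3 and 3.5.4, Table 2). Let d1 and d3 be the between-group differences in utility at months 1 and 3. The baseline difference is taken as 0, its expectation under randomisation.

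**Area over months 0 to 3, in years.**

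- Four-point rule: (3/12) × (0 + d3)/2 = d3/8.
- Five-point rule: (1/12) × d1/2 + (2/12) × (d1 + d3)/2 = d1/24 + d1/12 + d3/12 = d1/8 + d3/12.
- Shift from adding month 1: d1/8 + d3/12 − d3/8 = d1/8 − d3/24 = **0.125 × (d1 − d3/3)**.

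The segments from month 3 onward are the same under both rules and cancel. The shift is zero when d1 = d3/3, which is linear growth.

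**Relative size, assuming a constant difference d from month 3 to month 12.** The four-point gain is d/8 + (9/12)d = 0.875d. With d1 = f × d, the five-point gain is (0.75 + 1/12 + f/8)d.

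| d1 | Five-point gain | Four-point ÷ five-point | Four-point gain is |
|---|---|---|---|
| 0 | 0.833d | 1.050 | 5.0% too large |
| d/3 | 0.875d | 1.000 | equal |
| 0.5d | 0.896d | 0.977 | 2.3% too small |
| 0.75d | 0.927d | 0.944 | 5.6% too small |
| d | 0.958d | 0.913 | 8.7% too small |

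In the last row the cost-effectiveness ratio would be 0.958/0.875 = 1.095 times the five-point value for the same incremental cost, or 9.5% too high.

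**Absolute size.** No utility difference is given, so take d from 0.02 to 0.08 as an assumed range. With d1 between 0 and d, the shift runs from 0.125 × (0 − 0.02/3) = −0.0008 to 0.125 × (2/3) × 0.02 = +0.0017 QALY at d = 0.02, and from −0.0033 to +0.0067 QALY at d = 0.08.

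**A non-constant shape.** Section 3.11.3 gives pain differences from the earlier sham-controlled trial of 6.66, 9.59 and 6.97 at 12 weeks, 24 weeks and one year. Used only as a shape:

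- Four-point area: 6.66/8 + 0.25 × (6.66 + 9.59)/2 + 0.5 × (9.59 + 6.97)/2 = 0.83 + 2.03 + 4.14 = 7.00.
- If d1 = 0, the five-point area is 7.00 − 6.66/24 = 6.73, and the four-point area is 4.1% too large.
- If d1 = d3, it is 7.00 + 0.125 × (2/3) × 6.66 = 7.56, and the four-point area is 7.3% too small.

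The order of magnitude does not depend on the constant-difference assumption.

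**The case against.** The best defence is that section 9 is a short summary with a detailed plan to follow, that it nowhere says month 1 is deliberately excluded, and that the list may be a drafting slip. That lowers the seriousness but leaves the conflict in the text.

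A second defence is that month 1 is not core data: "The minimum core data set will include the MOxFQ and EQ-5D-5L at baseline and three months". It does not work, because months 6 and 12 are outside that core set as well and section 9 uses both.

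The objections to a stronger claim do stand. A reader might infer that the four-point rule certainly distorts the result, and does so where change is fastest. The documents do not support this:

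- The shift is zero under linear growth, and otherwise its sign depends on d1, for which there are no between-group data.
- The only one-month evidence is an uncontrolled case series of 31 people, which "found improvements in foot pain and disability at one and three months after wearing semi-rigid carbon fibre inserts" (section 2.4). It gives no effect size and no utility.
- The pain differences above imply an average change of 6.66/3 = 2.2 points per month up to 12 weeks, against (9.59 − 6.66)/3 = 1.0 over the next 12. But this is pain, and it says nothing about the shape inside the first three months.

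A reader might also suppose an early utility loss while people adapt to a rigid insert. Section 2.4 mentions a short-term difference in foot discomfort and blisters, which makes this conceivable, but it reports similar overall adverse event rates over three months (62% and 63%). A loss of 0.5d at month 1 would give a five-point gain of 0.771d and a four-point gain 13.5% too large. No figure in the protocol supports a loss of that size.

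Finally, the five-point trapezoid is itself an approximation. The percentages compare two rules, not a rule with the truth.

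**Conclusion.** The inconsistency is certain; the bias is possible, not shown. Section 9 uses four EQ-5D-5L time points for the QALY, three other places collect five, and nothing explains the difference.

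Relative to the five-point rule, the four-point QALY gain lies between about 5% too large and about 9% too small. This assumes a zero expected baseline difference, a constant difference from month 3, and d1 between 0 and d3. A month 1 difference outside that interval, including an early loss, would widen the range, but the protocol gives no utility data to size it.

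The effect is modest and confined to the economic evaluation. The primary outcome, the sample size and the clinical analyses are untouched. Nothing in the documents shows that the cost-effectiveness conclusion would change. The point is worth acting on because the better rule uses data the trial already plans to collect.

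**What to change.** Amend section 9 so that QALYs are computed by the trapezoidal rule from EQ-5D-5L at baseline, 1, 3, 6 and 12 months, in agreement with sections 3.5.3 and 3.5.4 and Table 2. Include month 1 utility in the multiple imputation model, so that a missed month 1 questionnaire does not remove a participant from the QALY analysis. Carry both into the health economic analysis plan before it is finalised.

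If there is a reason to keep four points, state it in section 9 and prespecify the five-point QALY as a sensitivity analysis.

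The cost is one phrase in the protocol and a matching line in the health economic analysis plan. Data collection, participant burden and sample size do not change.

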10.3 Sponsor and governance arrangements

University of Warwick is sponsor for this trial.

10.4 Ethical approval

All required ethical approval(s) for the trial will be sought using the Integrated Research Application System. The trial will be conducted in accordance with all relevant regulations.

Before enrolling patients into the trial, each trial site must ensure that the local conduct of the trial has the agreement of the relevant NHS Trust Research & Development (R&D) department. Sites will not be permitted to enrol patients into the trial until written confirmation of R&D agreement is received by Warwick Clinical Trials Unit.

Substantial protocol amendments (e.g. changes to eligibility criteria, outcomes, analyses) will be communicated by the trial team to relevant parties i.e. investigators, RECs, participants, NHS Trusts, trial registries, journals, as appropriate.

The REC and sponsor will be notified of the end of the study (whether the study ends at the planned time or prematurely). The CI will submit a final report with the results to the Funder by the end of the contract.

10.5 Trial Registration

The study will be registered on the International Standard Randomised Controlled Trial Number (ISRCTN) Register.

10.6 Trial non-compliances and serious breaches to GCP and/or trial protocol

Deviations from clinical trial protocols, GCP, and the formal requirements in place for a clinical trial occur commonly in clinical studies. The majority of these instances are technical deviations that do not result in harm to the trial subjects or significantly affect the scientific value of the reported results of the trial. Violation is a failure to comply with or variance from GCP and/or the final approved protocol. This results from error, fraud or misconduct. These cases should be documented in the non-compliance section of the case report form for the trial and appropriate corrective and preventative actions taken. Non-compliances will be included and considered when the clinical trial report is produced, as they may have an impact on the analysis of the data.

A "serious breach" is a breach which is likely to effect to a significant degree -

- (a) the safety or physical or mental integrity of the subjects of the study; or
- (b) the scientific value of the study

The sponsor will be notified immediately of any case where the above definition applies during the study conduct phase and will notify the licensing authority in writing of any serious breach of

- (a) the conditions and principles of GCP in connection with that study; or
- (b) the protocol relating to that study, as amended from time to time, within 7 days of becoming aware of that breach

10.7 Indemnity

NHS indemnity covers NHS staff, medical academic staff with honorary contracts, and those conducting the trial. NHS bodies carry this risk themselves or spread it through the Clinical Negligence Scheme for Trusts, which provides unlimited cover for this risk. The University of Warwick provides indemnity for any harm caused to participants by the design of the research protocol.

10.8 Trial timetable and milestones

Table 6: Trial Timeline

	Month	Recruitment
Start date	01-06-2024	n/a
Set-up	1-6	n/a
Internal pilot study	7-15	111
Main trial recruitment	16-26	438
Follow up	27-38	n/a
Analysis	39-42	n/a

10.9 Administration

The trial co-ordination will be based at WMS/WCTU, University of Warwick.

10.10 TMG

The TMG, consisting of the project staff and co-investigators involved in the day-to-day running of the trial, will meet regularly throughout the project. Significant issues arising from management meetings will be referred to the Trial Steering Committee or Investigators, as appropriate.

10.11 TSC

The trial will be guided by a group of respected and experienced personnel and trialists as well as at least one 'lay' representative. The TSC will have an independent Chairperson. Meetings will be held at regular intervals determined by need but not less than once a year. Routine business is conducted by email, post or teleconferencing.

The Steering Committee, in the development of this protocol and throughout the trial will take responsibility for:

- Major decisions such as a need to change the protocol for any reason
- Monitoring and supervising the progress of the trial
- Reviewing relevant information from other sources
- Considering recommendations from the DMC
- Informing and advising on all aspects of the trial

The membership of the TSC is shown on page 3. The membership of the TSC will be approved and appointed by the NIHR.

The full remit and responsibilities of the TSC will be documented in the Committee Charter which will be signed by all members.

10.12 DMC

The DMC will consist of independent experts with relevant clinical research, and statistical experience. The DMC will meet at the start of the study, potentially together with the TSC and regularly thereafter, as agreed with the committee. Confidential reports containing recruitment, protocol compliance, safety data and interim assessments of outcomes will be reviewed by the DMC. The DMC will advise the TSC as to whether there is evidence or reason why the trial should be amended or terminated.

The membership of the DMC is shown on page 3. The membership of the DMC will be approved and appointed by the NIHR.

DMC meetings will also be attended by the Chief Investigator and Trial Manager (for non-confidential parts of the meeting) and the trial statistician.

The full remit and responsibilities of the DMC will be documented in the Committee Charter which will be signed by all members.

10.13 Essential documentation

A Trial Master File will be set up according to Warwick SOP 11 and held securely at the coordinating centre.

The coordinating centre will provide Investigator Site Files to all recruiting centres involved in the trial.

10.14 Financial support

The trial has been funded by a contract award from the NIHR Health technology Assessment programme (NIHR157097)

10.15 Safeguarding researchers and research participants

The trial and all personnel working on it will comply with the University of Warwick's Safeguarding policy https://warwick.ac.uk/services/wss/safeguarding/

11. Monitoring, audit, and inspection

The study will be monitored by the trial team with support from the Quality Assurance team at WCTU as representatives of the Sponsor, study coordinating centre and academic lead, to ensure that the study is being conducted as per protocol, adhering to Research Governance and GCP. The approach to, and extent of, monitoring will be specified in a study monitoring plan determined by the risk assessment undertaken prior to the start of the study. A Trial Monitoring Plan will be developed and agreed by the TMG based on the study risk assessment, including on site monitoring if applicable. Sites will be expected to assist in monitoring the study. This may include hosting site visits, providing information for remote monitoring, or putting procedures in place to monitor the study internally. Processes to be considered in the monitoring plan will include participant enrolment, consent, eligibility, and allocation to study groups; adherence to study interventions and policies to protect participants, including reporting of harm and completeness, accuracy, and timeliness of data collection. The plan will be available from the study coordination centre. Whilst any on-site monitors work in the same institution as the study team (WCTU), they will act independently in this role.

12. Patient and public involvement (PPI)

This trial has been developed following in depth patient and public involvement. At the heart of the trial leadership we have two patient partners on our TMG, and PPI representatives on our TSC to provide oversight.

We will also create a wider and more diverse PPI reference group of people with experience of living with 1^{st} MTPJ OA.

Our patient partners and PPI representatives will be supported by the Chief Investigator, and PPI Lead, and through the peer support of lay partners on existing trials. Our patient partners are already experienced in their roles, being long standing members of the Keele Research User Group. Further training and support for all members is offered through WCTU and through University Hospitals Coventry and Warwickshire NHS Trust's R7D department who run regular lay seminars, group training, and other events through their Patient Research Advisory Group. All activity will be reimbursed at INVOLVE rates, for which there is adequate provision in the budget.

13. Dissemination and publication

The main report will be drafted by the trial co-ordinating team, and the final version will be agreed by the Trial Steering Committee before submission for publication.

The success of the trial depends on the collaboration of participants, clinicians, and researchers from across the UK. Authorship confers credit and has important academic, social, and financial implications. Authorship also implies responsibility and accountability for published work. Therefore, credit for contribution will be determined using the ICMJE Criteria for authorship, and non-author contributions will be acknowledged (https://www.icmje.org/recommendations/browse/roles-and-responsibilities/defining-the-role-of-authors-and-contributors.html).

Full results of the study will be prepared by the research team and lay partners and submitted to funders as a final report. Findings will be submitted to peer-reviewed journals and disseminated to the medical and exercise rehabilitation communities. We will publish papers in open-access journals including the study protocol, as per recommended guidance for transparent reporting, the Consolidated Standards of Reporting Trials (CONSORT) guidelines (www.consort-statement.org), the

BigTOE Trial Protocol

NIHR standard terms, and Warwick SOP 22: Publication & Dissemination. University of Warwick will review and approve all publications. We will submit abstracts to national and international conferences.

